4.2 Secondary Objectives

The secondary objectives of this study are to assess the percentage of subjects with virologic failure during treatment, to assess the percentage of subjects with post-treatment relapse, and to characterize the pharmacokinetics of DAAs including ritonavir, sofosbuvir, GS-331007 (predominant circulating metabolite of SOF), and RBV (if applicable) in adults with genotype 3 HCV infection.

5.0 Investigational Plan**5.1 Overall Study Design and Plan: Description**

This is a Phase 2, randomized, open-label, multicenter study evaluating the safety and efficacy of co-formulated ombitasvir/ABT-450/r co-administered with SOF with or without RBV in treatment-naïve and prior (pegIFN, RBV, and/or SOF) treatment-experienced adults with genotype 3 HCV infection without cirrhosis. Approximately 20 subjects will be enrolled across approximately 8 sites globally into one of two treatment arms ([Figure 1](#)).

Figure 1. Study Design

These subjects will be randomized to Arms A and B in a 1:1 ratio (approximately 10 subjects each). Randomization to Arms A and B will be stratified by IL28B genotype (CC versus non-CC) and prior treatment status (treatment-naïve versus treatment-experienced).

- **Arm A:** ombitasvir/ABT-450/r 25 mg/150 mg/100 mg and SOF 400 mg QD for 12 weeks
- **Arm B:** ombitasvir/ABT-450/r 25 mg/150 mg/100 mg and SOF 400 mg QD with RBV 1000 – 1200 mg BID for 12 weeks

RBV dosing will be weight-based, either 1000 mg or 1200 mg daily divided BID per local label (e.g., < 75 kg = 1000 mg daily divided BID or ≥ 75 kg = 1200 mg daily divided BID).

The duration of the study will be up to 60 weeks long (not including a screening period of up to 35 days) consisting of two periods: the Treatment Period and the Post-Treatment (PT) Period. All subjects who complete or prematurely discontinue the Treatment Period will be followed for 48 weeks to monitor safety, HCV RNA, the persistence of resistant viral mutants, and assessment of Patient Reported Outcomes (PROs).

Subjects will be either HCV treatment-naïve or previously treated with interferon, pegIFN, RBV, and/or SOF. Categorization of prior HCV treatment experience will be based on the last prior HCV treatment course. This prior HCV therapy must have been completed no less than 2 months prior to the Screening Visit.

Subjects whose only prior treatment experience included standard (non-pegylated) interferon will not be eligible. However, subjects with a prior history of non-pegylated interferon therapy who were subsequently treated with pegIFN/RBV, pegIFN/RBV plus SOF, or SOF plus RBV may be enrolled.

Subjects with previous HCV RNA measurements that provide complete documentation of the type of response to prior treatment with pegIFN/RBV without sofosbuvir, pegIFN/RBV plus sofosbuvir, or sofosbuvir plus RBV therapy will be categorized as one of the following:

- Prior pegIFN/RBV null-responder: failed to achieve a $1 \log_{10}$ IU/mL reduction in HCV RNA by Week 4 or a $2 \log_{10}$ IU/mL reduction in HCV RNA by Week 12 during a prior pegIFN/RBV treatment course;
- Prior pegIFN/RBV partial responder: achieved at least a $2 \log_{10}$ IU/mL reduction in HCV RNA by Week 12 during a prior pegIFN/RBV treatment course, but failed to achieve HCV RNA undetectable at the end of treatment;
- Prior SOF breakthrough/non-responder: HCV RNA quantifiable at the end of treatment with SOF plus pegIFN/RBV, or SOF plus RBV;
- Prior HCV therapy relapser: achieved HCV RNA unquantifiable (detected or undetected) at end of a prior treatment course of pegIFN/RBV, SOF plus pegIFN/RBV, or SOF plus RBV, but HCV RNA was quantifiable following cessation of therapy.

Subjects treated with pegIFN/RBV without SOF, pegIFN/RBV plus SOF, or SOF plus RBV therapy with a less well-characterized treatment experience, including those subjects with incomplete HCV RNA and treatment date documentation, will require approval by

the AbbVie Study Designated Physician for the determination of study eligibility. These subjects will be categorized as one of the following:

- Prior HCV therapy relapse/breakthrough: Achieved at least one documented result of HCV RNA unquantifiable (detected or undetected) during a prior treatment course of pegIFN/RBV, SOF plus pegIFN/RBV, or SOF plus RBV;
- Prior HCV therapy non-responder: No documented result of HCV RNA unquantifiable (detected or undetected) during a previous treatment with pegIFN/RBV, SOF plus pegIFN/RBV, or SOF plus RBV treatment with insufficient data available to distinguish between breakthrough, partial, and null responder;
- pegIFN intolerant (Category does not apply to subjects previously treated with SOF plus RBV): Did not meet any definitions of treatment-failure and discontinued pegIFN-containing therapy prior to a full course of treatment due to pegIFN intolerance.
- pegIFN experienced – other (Category does not apply to subjects previously treated with SOF plus RBV): Includes pegIFN/RBV or SOF plus pegIFN/RBV experienced subjects who do not have adequate documentation of response to be included in any of the above categories.

5.1.1 Screening

At the Screening Visit, subjects who provided written (signed and dated) informed consent prior to any study specific procedures, will receive a unique subject number via an Interactive Response Technology (IRT) system and will undergo the study procedures indicated within the Study Activities table and detailed in Section [5.3.1.1](#) associated with the Screening Visit. The investigator will evaluate whether the subject meets eligibility criteria, as specified in Section [5.2.1](#) and Section [5.2.2](#). The informed consent process and all screening procedures performed will be recorded and documented. Eligible subjects have up to 35 days following the Screening Visit to enroll into the study. Subjects who require a liver biopsy to determine eligibility should meet all of the other inclusion and none of the exclusion criteria before undergoing a liver biopsy.

The study was designed to enroll approximately 20 subjects to meet scientific and regulatory objectives without enrolling an undue number of subjects in alignment with ethical considerations. Therefore, if the target number of subjects has been enrolled, there is a possibility that additional subjects in screening will not be enrolled.

5.1.1.1 Rescreening

Subjects who meet all eligibility criteria with the exception of up to three exclusionary laboratory parameters may rescreen once within the 35-day screening period without prior AbbVie approval. However, subjects with any of the following exclusionary values will not be allowed to rescreen: exclusionary HCV genotype, a positive hepatitis B surface antigen (HBsAg), positive human immunodeficiency virus (HIV) antibody, or confirmed pregnancy. Subjects with more than three exclusionary laboratory results will require approval from the AbbVie Study Designated Physician prior to rescreening. Subjects being rescreened because of exclusionary laboratory parameter(s) must have the related panel(s) repeated (e.g., exclusionary hemoglobin requires a repeat hematology panel) within the same screening period.

For subjects who do not meet the study eligibility criteria, the site personnel must register the subject as a screen failure in both IRT and electronic data capture (EDC) systems.

5.1.2 Treatment Period

Non-cirrhotic subjects with HCV genotype 3 infection who meet the eligibility criteria will be randomized via IRT in a 1:1 ratio to either ombitasvir/ABT-450/r co-administered with SOF (Arm A) or ombitasvir/ABT-450/r co-administered with SOF and RBV (Arm B). The Treatment Period of the study consists of 12 weeks of open-label treatment.

All DAAs will be administered once daily (QD) as detailed below.

- ombitasvir/ABT-450/r 25 mg/150 mg/100 mg QD
- SOF 400 mg QD

RBV dosing, if applicable, will be weight based, either 1000 mg or 1200 mg daily divided BID per local label (e.g., < 75 kg = 1000 mg daily divided BID or \geq 75 kg = 1200 mg daily divided BID).

Subjects will receive instructions regarding study drug administration and dosing and will be administered the first doses of study drugs at the site on Study Day 1. All subjects will continue to return to the site on an outpatient basis through the end of their Treatment Period for study procedures as identified in [Table 4](#); site personnel should make every reasonable effort to ensure visit schedule adherence. It should be noted and reinforced to subjects that SOF is supplied with the exact amount of tablets needed between the study drug dispensation visits in [Table 4](#). Subjects who cannot complete study visits according to schedule will need assistance in managing their study drug supply between visits to ensure they do not run out of study drugs prior to their next study visit.

Safety and efficacy evaluations will occur through the study. As this is an open-label study, the safety data will be reviewed by AbbVie during the Treatment Period of the study. Virologic failure criteria for subject management, as detailed in Section [5.4.1.1](#), will be evaluated and applied by the investigator.

Plasma samples for pharmacokinetic analysis will be collected as detailed in Section [5.3.2.1](#).

Safety and tolerability of the treatments will be assessed throughout the study. Laboratory testing will include chemistry, hematology, and urinalysis ([Table 6](#)). Ongoing review of the data is planned in order to determine if subjects meet the virologic failure criteria (Section [5.4.1.1](#)). Virologic failure criteria will be evaluated and applied by the Investigator as detailed in Section [5.4.1.1](#).

Subjects who prematurely discontinue from the Treatment Period should return for a Treatment Discontinuation Visit and undergo the study procedures as defined in [Table 4](#) and as described in Section [5.4.1](#). Ideally, this should occur on the day of the study drug discontinuation, but is recommended to be no later than 2 days after their final dose of

study drugs and prior to initiation of any other anti-HCV therapy. Subjects who complete or prematurely discontinue study drug will immediately start the PT Period and be monitored for safety, virologic failure, and resistance as detailed in Section 5.4.1.1.

5.1.3 Post-Treatment (PT) Period

All subjects who receive at least one dose of study drugs will be monitored for safety, HCV RNA, the emergence and/or persistence of resistance viral variants, and assessment of PROs for an additional 48 weeks following the last dose of study drugs. Subjects will return to the study site as outlined in Table 5 for PT procedures. The PT Period will begin the day after the last dose of study drugs. Subjects who prematurely discontinue the PT Period should return to the site for a PT Discontinuation Visit as outlined in Table 5.

5.2 Selection of Study Population

The subject population consists of HCV genotype 3-infected treatment-naïve and prior (pegIFN, RBV, and/or SOF) treatment-experienced adult subjects without cirrhosis. Subjects who meet all the following inclusion criteria and who do not meet any of the following exclusion criteria will be eligible for enrollment into the study.

5.2.1 Inclusion Criteria

1. Male or female at least 18 years of age at time of screening.
2. Female who is:
 - practicing total abstinence from sexual intercourse (minimum 1 complete menstrual cycle); or
 - sexually active with female partners only; or
 - not of childbearing potential, as defined as:
 - postmenopausal for at least 2 years prior to screening (defined as amenorrheic for longer than 2 years, age appropriate and confirmed by a follicle-stimulating hormone (FSH) level indicating a postmenopausal state); or

- surgically sterile (defined as bilateral tubal ligation, bilateral oophorectomy or hysterectomy) or has a vasectomized partner(s); or
- of childbearing potential and sexually active with male partner(s):
 - currently using at least one effective method of birth control at the time of screening and agrees to practice two effective methods of birth control while receiving study drugs (as outlined in the subject information and consent form or other subject information documents),

For subjects whose study drug regimen will not include RBV, contraceptive practices must start on Study Day 1 and must continue for 30 days after stopping study drugs.

For subjects whose study drug regimen will include RBV, the contraceptive practices must start on Study Day 1 and must continue for 7 months after stopping study drug, or as **directed by the local ribavirin label**.

(Note: Estrogen-containing hormonal contraceptives, including oral, injectable, implantable, patch and ring varieties, may not be used during study drug treatment).

3. Females must have negative results (unless otherwise noted below) for pregnancy tests performed:

- at Screening by serum specimen within 35 days prior to initial study drug administration, and
- at Baseline (prior to dosing) by urine specimen

Female subjects with a borderline human chorionic gonadotropin (hCG) result at Screening and/or Day 1 may enroll into the study if they either:

- have a documented history of bilateral tubal ligation, hysterectomy, bilateral oophorectomy; or
- are confirmed to be postmenopausal defined as amenorrheic for longer than 2 years, age appropriate, and confirmed by a FSH level indicating a postmenopausal state at Screening.

4. Males who are not surgically sterile who are sexually active with female partner(s) of childbearing potential, must agree to practice two effective forms of birth control (as outlined in the subject information and consent form or other subject information documents).

For subjects whose study regimen includes RBV, the contraceptive practices must be observed from Study Day 1 and must continue for 7 months after stopping study drug, or as directed by the local RBV label.

For subjects whose study regimen does not include RBV, these contraceptive practices must start on Study Day 1 and must continue until 30 days after stopping study drugs.

5. Subjects must be able to understand and adhere to the study visit schedule and all other protocol requirements and must voluntarily sign and date an informed consent.
6. Body Mass Index (BMI) is from ≥ 18 to $< 38 \text{ kg/m}^2$ at the time of screening. BMI is calculated as weight measured in kilograms (kg) divided by the square of height measured in meters (m).
7. Chronic HCV infection prior to study enrollment. Chronic HCV infection is defined as one of the following:
 - Positive for anti-HCV Antibody (Ab) or HCV RNA at least 6 months before Screening, and positive for HCV RNA and anti-HCV Ab at the time of Screening; or
 - HCV RNA $> 10,000 \text{ IU/mL}$ at the time of Screening with a liver biopsy consistent with chronic HCV infection (or a liver biopsy performed prior to enrollment with evidence of chronic hepatitis C disease).
8. Screening laboratory results from the central laboratory indicating HCV genotype 3 infection only.
9. Absence of cirrhosis, as documented by meeting one of the following criteria (per local standard practice):

- A liver biopsy within 24 months prior to or during screening demonstrating the absence of cirrhosis;
- Only in the absence of a biopsy within the 24 months prior to screening or during screening:
 - a Screening FibroTest score of ≤ 0.72 and Aspartate Aminotransferase to Platelet Ratio Index (APRI) ≤ 2 ; or
 - a Screening transient elastography (e.g., FibroScan[®]) results of < 12.5 kPa.

Subjects with a FibroScan result that is ≥ 12.5 kPa and < 14.6 KPa, **or** a FibroTest result that is ≤ 0.72 and an APRI > 2 , **or** a FibroTest result that is > 0.73 and an APRI ≤ 2 must have a liver biopsy performed within 24 months prior to screening showing no evidence of cirrhosis, or in the absence of an available biopsy result within 24 months prior to screening, may undergo a liver biopsy during screening to rule out cirrhosis. The result of the liver biopsy will be considered the decisive result for study eligibility and subjects may be enrolled as non-cirrhotic only if the biopsy performed within the previous 24 months or during the Screening period shows no evidence of cirrhosis.

Rationale for Inclusion Criteria

1, 7 – 9	To select the appropriate subject population with sufficient disease severity for evaluation
6	For the safety of study subjects
2 – 4	RBV has known teratogenic effects
5	In accordance with Good Clinical Practice (GCP)

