5.2.3.3 Prohibited Therapy

Subjects must be able to safely discontinue any prohibited medications within 2 weeks or within 10 half-lives of the respective medication/supplement (if known), whichever is longer, prior to initial study drug administration through 2 weeks following discontinuation of study drugs. Subjects must be consented prior to discontinuing any prohibited medications for the purpose of meeting study inclusion criteria.

In addition to the medications listed in [Table 3](#), use of known strong inducers of CYP3A or strong inhibitors or inducers of P-glycoprotein is prohibited within 2 weeks of the respective medication/supplement prior to the initial dose of study drug through the first 2 weeks after the subject has completed study drugs.

Refer to the current local labels for ritonavir, RBV, and SOF for a list of prohibited medications. Anti-HCV medications other than those specified in the protocol will not be allowed during the treatment period of the study.

Contraceptives

Prior to enrollment, subjects should agree to practice two effective methods of birth control while receiving study drugs starting with Study Day 1 and for 7 months after stopping study drug or as directed by the local ribavirin label. Subjects using systemic estrogen-containing contraceptive therapy (including estrogen-containing oral contraceptives) have a higher risk for elevated ALT levels. Subjects using these medications must discontinue them at least 2 weeks prior to study drug administration or 10 half-lives (if known), whichever is longer. Subjects may replace the systemic

estrogen-containing contraceptive with a progestin-only hormonal contraceptive method. Estrogen-containing contraceptives may be resumed 2 weeks after the last dose of DAAs.

Use of hematopoietic growth factors is not permitted during this study without the approval of the AbbVie Study Designated Physician. Management of hematologic growth factor therapy is the responsibility of the investigator; growth factors will not be provided by AbbVie, and AbbVie will not reimburse for the expense of growth factors or their use.

Investigators should refer to the package inserts for erythropoiesis stimulating agents for additional information regarding their use.

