- g. Evaluate the Screening ECG prior to dosing to determine eligibility.
- h. Urine pregnancy test is not required after the Day 1 Visit for female subjects with a documented history of bilateral tubal ligation, bilateral oophorectomy or hysterectomy or who are confirmed to be post-menopausal. A positive urine pregnancy test requires a confirmatory serum test.
- i. For subjects who have not had a qualifying liver biopsy within the previous 24 months.
- j. If the optional pharmacogenetic sample is not collected at Study Day 1, it may be collected at any other visit during the study. Verify subject has given consent to pharmacogenetic testing.
- k. Protocol-related nonserious adverse events will be collected from the time the subject signed the study-specific informed consent until study drug administration.
- l. EuroQol 5 Dimensions 5 Levels Health State Instrument (EQ-5D-5L) and Fatigue Severity Scale (FSS) should be administered before any study procedures and in the order listed.
- m. PK samples will be collected at 2, 4, and 6 hours post-DAA dose at Day 1. Additional intensive PK samples will be collected at the Week 2 study visit where samples will be collected at pre-dose and approximately 2, 4, and 6 hours post-DAA dose. On the day of intensive blood sampling, subjects will take their morning dose of DAs and ribavirin onsite in the presence of study site personnel and the time of administration will be recorded to the nearest minute.

Table 5. Study Activities – Post-Treatment (PT) Period

Activity	PT Wk 2	PT Wk 4	PT Wk 8	PT Wk 12	PT Wk 24	PT Wk 36	PT Wk 48 or PT D/C
Vital Signs and Weight	X	X	X	X	X	X	X
Hematology/Chemistry/Urinalysis/Coagulation Panel		X		X			
Monthly Pregnancy Test (females) ^a		X	X				(Weeks 12, 16, 20, 24, 28)
PRO Instruments ^b		X	X	X	X	X	X
Concomitant Medication Assessment ^c	X	X	X	X	X	X	X
Adverse Event Assessment ^d	X	X	X				
HCV RNA Samples	X	X	X	X	X	X	X
HCV Resistance Sample	X	X	X	X	X	X	X
Archive Plasma Sample	X	X	X	X	X	X	X
Archive Serum Sample	X	X	X	X	X	X	X
IP-10 Sample					X		X
mRNA Sample (Optional)		X			X		

Wk = Week; PT D/C = Post-Treatment Discontinuation

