- The investigator will repeat the test to verify the out-of-range value.
- The investigator will follow the out-of-range value to a satisfactory clinical resolution.

- A laboratory test value that requires a subject to be discontinued from the study or study drugs or requires a subject to receive treatment that will be recorded as an adverse event.

The management of laboratory abnormalities that may occur during the study is described in Section [6.7](#).

Pregnancy Test

A urine pregnancy test will be performed for all female subjects at all visits specified in [Table 4](#) and [Table 5](#). In addition, a serum pregnancy test will be performed at Screening and Study Day 1 Visits and analyzed by the central laboratory. All urine pregnancy tests will be performed on-site during the study visit if there is a scheduled visit, as specified in [Table 4](#) and [Table 5](#). A positive urine pregnancy test requires a confirmatory serum test. Urine pregnancy tests are not required after Day 1 for female subjects with a documented history of bilateral tubal ligation, bilateral oophorectomy, hysterectomy, or for subjects who are confirmed to be postmenopausal. Confirmation of postmenopausal status will be determined during the Screening period, based on the subject's history, and measured by FSH.

For subjects on a RBV-inclusive regimen where there is not a scheduled study visit, female subjects of childbearing potential may either have PT Period pregnancy testing performed at the site as an unscheduled visit using an unscheduled visit test kit or a urine pregnancy test may be conducted by the subject at home with a pregnancy test kit provided by the site; site personnel should contact these female subjects to capture the results of any study-related pregnancy tests performed at home. The pregnancy test results will only be recorded in the subject's source records.

If the subject elects to return to the study site for an unscheduled visit for pregnancy testing, the results of the urine pregnancy test will be recorded on the eCRF, unless serum pregnancy test is elected. Serum pregnancy testing will be completed by the central laboratory and loaded into the clinical database.

Hepatitis and HIV Screen

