6.6 Pregnancy

Subjects and their partners should avoid pregnancy and males should avoid sperm donation throughout the course of the study, starting with Study Day 1 and for 30 days after the end of treatment with DAAs only, or for 7 months after the last dose of RBV (or per local RBV label) and/or consistent with local treatment guidelines for RBV.

Pregnancy in a study subject must be reported to the AbbVie within 1 working day of the site becoming aware of the pregnancy. Subjects receiving a RBV-inclusive regimen who report a positive pregnancy test during the Treatment Period must be notified to stop RBV immediately. Administration of DAAs may be continued at the investigator's discretion, if the benefit of continuing therapy is felt to outweigh the risk (Section [5.4.1](#)).

Information regarding a pregnancy occurrence in a study subject and the outcome of the pregnancy will be collected for pregnancies occurring up to 30 days after the end of treatment with DAAs only, or 7 months (or per local RBV label) after the last dose of RBV for treatment with DAAs plus RBV. The investigator is encouraged to report the pregnancy information to the voluntary RBV Pregnancy Registry, if RBV is included within the regimen.

Subjects who discontinue study medications due to pregnancy will be monitored for SVR in the Post-Treatment Period as described in Section [5.1.3](#).

Pregnancy in a study subject is not considered an adverse event. However, the medical outcome of an elective or spontaneous abortion, stillbirth, or congenital anomaly is considered a serious adverse event and must be reported to AbbVie within 24 hours of the site becoming aware of the event.

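### The protocol's sections disagree on whether a woman with a vasectomised partner is of childbearing potential and, separately, on how long contraception lasts after the ribavirin-free regimen

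*Protocol*

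**What the plan says.** Inclusion criterion 2 (Protocol Section 5.2.1) sets alternative branches for women: abstinent, sexually active with female partners only, "not of childbearing potential, as defined as", or "of childbearing potential and sexually active with male partner(s"). The third branch covers confirmed menopause and the item "surgically sterile (defined as bilateral tubal ligation, bilateral oophorectomy or hysterectomy) or has a vasectomized partner(s"). Only the fourth branch carries the condition that the woman "agrees to practice two effective methods of birth control while receiving study drugs". The rationale table at the end of Section 5.2.1 justifies criteria 2 to 4 by ribavirin's teratogenicity.

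Other sections bear on the same woman:

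- Section 5.2.3.3 (Contraceptives) says that, before enrolment, "subjects should agree to practice two effective methods of birth control while receiving study drugs starting with Study Day 1 and for 7 months", counted from the end of dosing, with the local ribavirin label as the alternative. It has no exemption and no split by regimen.
- Table 4 note h says "Urine pregnancy test is not required after the Day 1 Visit for female subjects with a documented history of bilateral tubal ligation", then adds oophorectomy, hysterectomy and confirmed menopause. Table 5 note a, Table 6 note d and the Pregnancy Test text in Section 5.3.1.1 use the same list. The borderline-hCG allowance in criterion 3 uses those conditions too.
- Section 5.3.1.1 says that, on a ribavirin regimen where no visit is scheduled, "female subjects of childbearing potential may either have PT Period pregnancy testing performed at the site as an unscheduled visit", or may test at home.
- Section 6.6 sets the period of pregnancy avoidance as "for 30 days after the end of treatment with DAAs only, or for 7 months after the last dose of RBV" (or per local label).

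**The concern.** Childbearing potential is a property of the subject. A vasectomised partner may be relevant to her risk of conceiving, but it does not change her own fertility, and it depends on someone who is not in the trial. Placing it inside the definition matters because the protocol uses the term again, in deciding who agrees to two contraceptive methods and in describing who may use the off-visit post-treatment tests. A site that applies criterion 2 literally and a site that applies Section 5.2.3.3 literally would ask different things of the same woman.

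The second disagreement concerns duration. At the point where a subject agrees to a contraception period, the protocol gives two lengths for the regimen without ribavirin.

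At stake are consistent instructions to sites and consistent undertakings by subjects, in a trial whose own reason for these criteria is ribavirin's teratogenicity. No endpoint, analysis population or precision statement depends on it.

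**Working it through.** There is no planned figure to reproduce. The check sets the passages side by side.

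**Step 1: the woman with a vasectomised partner who is otherwise fertile**

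| Place in the protocol | How it applies to her |
|---|---|
| 5.2.1, criterion 2 | Classed as not of childbearing potential; no two-method agreement attached |
| 5.2.1, criterion 3 (borderline hCG) | Not among those allowed |
| 5.2.3.3, Contraceptives | Two methods, as for all subjects |
| Table 4 note h, Table 5 note a, Table 6 note d | Not exempt from urine tests after Day 1 |
| 5.3.1.1, Pregnancy Test, general rule | Tested, as are all female subjects at the visits in Tables 4 and 5 |
| 5.3.1.1, off-visit tests on ribavirin | Worded for women of childbearing potential, a class that criterion 2 places her outside |
| Table 5 note a, off-visit tests on ribavirin (post-treatment Weeks 16, 20, 28) | Worded for subjects on ribavirin, with no such limit |
| 6.6 | Avoid pregnancy, as for all subjects and their partners |

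The first row conflicts directly with the third: criterion 2 attaches no two-method agreement and Section 5.2.3.3 requires one. The sixth and seventh rows describe the same tests with different scope. The Table 5 row itself is for females and runs through post-treatment Week 28, so the schedule still includes her; what is unclear is whether the off-visit arrangement in Section 5.3.1.1 is meant for her.

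The vasectomy item shares a sentence with surgical sterility, so its place under this heading is not an effect of lost indentation in the text extraction. It appears nowhere else in the protocol.

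**Step 2: length of the post-treatment period**

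| Section | Without ribavirin | With ribavirin |
|---|---|---|
| 5.2.1, criteria 2 (women) and 4 (men) | 30 days | 7 months or local label |
| 5.2.3.3 | 7 months or local ribavirin label (no split) | 7 months or local label |
| 6.6 | 30 days | 7 months or local label |

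Taking 7 months as about 213 days, the gap in the ribavirin-free column is 213 − 30 = 183 days. A local ribavirin label with a different period would change that figure. In the ribavirin column the lengths agree; only the starting point differs, since Sections 5.2.1 and 5.2.3.3 count from stopping study drug and Section 6.6 counts from the last ribavirin dose.

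**Step 3: how many subjects**

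The duration conflict applies to Arm A, about 10 subjects in the protocol. The vasectomised-partner clause could apply in either arm. Neither document gives the number of women expected or the number who would enter by this clause.

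**The case against.** The strongest reply is that the protocol is less inconsistent than it looks. Abstinent women and women with female partners only also meet criterion 2 without the two-method agreement and are also absent from every testing exemption. A lighter contraception duty with continued testing is therefore a general pattern, and the exemption lists need not mirror criterion 2. Much of this stands: absence from an exemption list does not show that the protocol regards a woman as fertile, and no other section names the woman with a vasectomised partner. But the abstinent and female-partner branches are not labelled as lacking childbearing potential. Hers is, and Section 5.3.1.1 uses that label when describing the off-visit tests. The pattern also does not resolve the conflict with Section 5.2.3.3, which makes no exception.

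A second reply is that 7 months in Section 5.2.3.3 is a precaution, because agreement comes before enrolment and the arm is assigned on Day 1. That reading is possible but unstated, and criteria 2 and 4, which also apply before the arm is known, do split by regimen.

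A reader might infer three stronger things, and the documents support none of them.

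- That she gives no contraception commitment at all. Section 5.2.3.3 read literally still binds her, Section 6.6 asks all subjects and their partners to avoid pregnancy, and criterion 2 refers to consent and subject information documents for details of birth control; those documents are not available here.
- That she is left out of the scheduled pregnancy tests. Section 5.3.1.1 and Tables 4 and 5 keep her in them.
- That a ribavirin subject is unprotected for 84 + 213 = 297 days. That sum is treatment plus follow-up time; it measures no risk, and it ignores both the vasectomy that brings her under the clause and the local-label alternative.

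**Conclusion.** The protocol contradicts itself on two separate points. First, criterion 2 treats a partner's vasectomy as the subject's own lack of childbearing potential and so attaches no two-method agreement to her, while Section 5.2.3.3 requires one of every subject; in addition, the scope of the off-visit post-treatment tests on ribavirin is unclear for her. Second, for the ribavirin-free regimen, Section 5.2.3.3 gives a period about 183 days longer than Sections 5.2.1 and 6.6. This second point does not extend to the length of the period for the ribavirin arm, so it should not be read as conflicting durations under teratogenic exposure.

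The conclusion rests on the wording of the protocol alone, with 7 months taken as 213 days for the size of the gap. The consent form may already settle some of it. The SAP describes a larger design, with ribavirin in Arms B to E (about 10 + 10 + 10 + 20 = 50 of about 70 subjects). Whether the protocol for that design kept this wording is unknown; if it did, more subjects would be concerned. The SVR₁₂ analysis and the sample-size statement are unaffected. The point is worth correcting because it governs what subjects agree to and which women sites classify as able to conceive.

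**What to change.** Reconcile criteria 2, 3 and 4 in Section 5.2.1, the Contraceptives text in Section 5.2.3.3, Table 4 note h, Table 5 note a, Table 6 note d, the Pregnancy Test text in Section 5.3.1.1, and Section 6.6, so that:

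- one definition of childbearing potential governs eligibility, contraception and testing, and states explicitly where a woman with a vasectomised partner falls;
- Section 5.3.1.1 and Table 5 note a describe the same group for the off-visit post-treatment tests;
- each regimen has one stated post-treatment duration, with one starting point.

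Which definition, rule and duration apply is for the sponsor to decide. The cost is protocol wording, with matching consent and subject information text where needed. Reconciling the text does not in itself add a visit or a type of test, and it needs no change to the SAP.
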